5.1.2 STOPPING RULES

The Sponsor, Investigator (following consultation with the Sponsor), or regulatory officials (regulatory agency or an Institutional Review Board [IRB]/ Independent Ethics Committee [IEC]) have the right to prematurely discontinue or suspend the study or investigational site at their discretion, at any time, if study and/or site conditions warrant. This action may be taken after appropriate consultation among the Sponsor, Investigator, and clinical monitor. The reasons for such action may include, but are not limited to the following:

- Safety concerns, such as more than one third of the patients within a dose cohort have one of the following:
 - \geq Grade 3 systemic infusion reactions (despite pre-medication),
 - Grade 4 DLTs (Refer to Protocol Section 6.2), or
 - Related serious adverse events (SAEs) (Refer to Protocol Section 8.2.3 & 8.3.1.1)
- The Investigator does not comply with the protocol, Good Clinical Practice (GCP), and/or any contract between the Investigator and Sponsor, including Contract Research Organizations (CROs) and subsidiaries thereof.

In the circumstance of such an event, the Sponsor reserves the right to halt and review this study and will discuss with the Investigator (including the reasons for taking such action) about dose modification, amendment to protocol, or study stopping. Final decision about continuing, termination or any other change in the study would remain with the Sponsor.

5.1.3 PART B-COHORT-EXPANSION

Up to 57 additional patients with advanced solid tumors that have high Globo H expression (defined as an H-score ≥ 100 using a validated immunohistochemistry [IHC] assay) will be enrolled in Part B using a Simon's two-stage cohort expansion design. Part B will be conducted to obtain additional safety data, characterize the PK profile of OBI-999, and obtain a preliminary assessment of the clinical activity profile of OBI-999 in Globo H expressing advanced solid tumors.

Patients enrolled in Part B will receive the RP2D dose of 1.2 mg/kg (capping calculations at a maximum of 100 kg) OBI-999 on Day 1 of each 21-day cycle.

The following 3 cohorts of patients who have high expression of Globo H by a qualified laboratory assessment (Globo H H-score ≥ 100 using a validated IHC assay) will be enrolled in Part B.

- Cohort 1: Pancreatic cancer
- Cohort 2: Colorectal cancer
- Cohort 3: Basket (any solid tumor types other than those included in Cohorts 1 and 2)

Patients will continue to receive treatment with OBI-999 until disease progression, unacceptable toxicity, consent withdrawal, or for up to 35 cycles (approximately 2 years), whichever occurs first.

5.1.4 STUDY DURATION

The study (Parts A and B) will include a screening period (up to 28 days), a treatment period, and a follow-up period.

Patients will continue to receive treatment with OBI-999 until disease progression, unacceptable toxicity, consent withdrawal, or for up to 35 cycles (approximately 2 years), whichever occurs first. Patients will be followed up to the 24-week scheduled response assessment for the purposes of counting objective responses for Simon's two-stage design success criteria.

The safety follow-up visit will be conducted 28 days after the last dose of study treatment.

5.2 STUDY TREATMENT

For Part A (Dose-Escalation), OBI-999 was planned to be given at doses of 0.4, 0.8, 1.2, 1.6, and 2.0 mg/kg (capping calculations at a maximum of 100 kg) using a 3+3 design to identify the MTD and RP2D.

For Part B (Cohort-Expansion), OBI-999 will be given at the RP2D of 1.2 mg/kg (capping administered dose to a maximum of 120 mg for 100 kg).

OBI-999 investigational drug solution (OBI-999 drug product mixed with saline/glucose infusion solution) will be administered on Day 1 of each 21-day cycle by the site staff. The infusion should be given for a duration of approximately 60 minutes (± 10 minutes), for the initial 2 cycles (Cycle 1 and Cycle 2). The infusion duration for Cycles 3 and beyond may be reduced, at the Investigator's discretion, to 30 minutes if no infusion related AEs occur during the first 2 cycles.

Treatment will continue until disease progression, unacceptable toxicity, consent withdrawal, or for up to 35 cycles (approximately 2 years), whichever occurs first.

5.3 SAFETY REVIEW COMMITTEE

The safety review committee (SRC) for this study will be comprised of the clinical lead, medical monitor, and the Investigator(s) or designee. The SRC will act in an advisory capacity to monitor

patient safety and efficacy during the trial and its activities will be defined in a separate SRC charter.

This SRC convened after each cohort completed the first cycle of treatment during Part A (Dose-Escalation), to review safety data (AEs and laboratory toxicities) and to determine whether DLTs occurred.

The RP2D for Part B (Cohort-Expansion) was determined by the SRC based on both the frequency of DLTs observed during Cycle 1 according to the 3+3 design, and also by the frequency and severity of cumulative toxicities such as peripheral neuropathy. The SRC will continue to monitor the severity and frequency of acute and cumulative toxicities at regular intervals, i.e., every 3 months, to ensure acceptable tolerability of the selected RP2D and of the effectiveness of dose modification rules. The SRC will receive updated tabulations of recruitment, AEs, SAEs, clinical laboratory events, and dose modifications which will serve as the basis for their assessments.

5.4 INTERIM ANALYSIS

There will not be any other formal interim analyses except for the one related to Simon's two stage design described below; however, a description of the Dose-Escalation Phase and the selection of the RP2D may be written up for the purposes of a manuscript.

Moreover, the cohort expansion portion of the study (Part B) will enrol up to 57 patients based on Simon's two-stage design. The first stage will recruit up to 9 patients in each of three cohorts. If at least one objective response is observed, a second stage recruitment will occur with up to 10 additional patients enrolled into that cohort, for a total of up to 19 patients per cohort. If at least 4 objective responses are observed in the 19 patients, then OBI-999 will be considered worthy of further evaluation in that indication. Patients will be followed up to the 24-week scheduled response assessment for the purposes of counting objective responses for Simon's two-stage design success criteria. A formal analysis will be performed to support it.

Patient enrolment, patient disposition, baseline characteristics, cancer history, clinical benefit rate, exposure to OBI-999, AE and ECG summaries (all described in this document) will support this formal analysis at end of stage 1.

If Simon's two-stage design success criteria is not met, then the second stage recruitment will not occur, and analyses will be done for supporting an aCSR.

The description above represents the initial interim analysis planning based on the protocol. In reality at the end of the first stage of Part B, four patients did not have a RECIST post-baseline assessment and so it has been decided to replace them to have enough data to perform the go/no-go analysis. 2 'replacement' patients have been enrolled in the pancreatic cohort, while searching for 2 'replacement' patients in the colorectal cohort was in progress. On 10th November 2023, Sponsor stated they stop the study and elected to generate an aCSR and so formal go/no-go analysis never happened.

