10. ANALYTICAL PLAN AND STATISTICAL METHODS

10.1 GENERAL CONVENTIONS AND STATISTICAL CONSIDERATIONS

All statistical analyses will be performed, and data appendices will be created using the SAS system version 9.4 or higher.

Data collected in this study will be presented in patient data listings and summary tables.

Descriptive statistics (number of patients with non-missing values, mean, standard deviation [SD], median, minimum, and maximum) will be presented for continuous variables. All raw data will be presented to the original number of decimal places. Means and medians will be presented to 1 more decimal place than in the raw data. Standard deviations will be presented to 2 more decimal places than in the raw data. Descriptive summaries of time to event data will include medians and confidence intervals.

All data will be listed for all patients.

Frequency distributions (counts and percentages) together with mean and SD of ordinal scores will be presented for categorical variables. Discrete variables that are ordinal scaled (e.g., Eastern Cooperative Oncology Group [ECOG] performance score) will additionally be presented with mean scores and SD. If not specified otherwise, the number of observations with non-missing values will be the denominator for percentage calculation. Further details on the handling of missing observations are given in section 9.3.

If days are converted to months, a factor of 30.4 days/month will be used. If days are converted to years, a factor of 365.25 days/year will be used. Time will be shown in study weeks, i.e., number of weeks from the first administration of any study drug.

Dose-Escalation (Part A). The dose-escalation analysis will be presented by OBI-999 dose (0.4, 0.8, 1.2, and 1.6 mg/kg) cohorts and overall. The following cohorts and overall will be presented:

- OBI-999 0.4 mg/kg
- OBI-999 0.8 mg/kg
- OBI-999 1.2 mg/kg
- OBI-999 1.6 mg/kg
- Dose-Escalation Total

OBI-999 2.0 mg/kg was planned but Part A was closed before this dose was administered, and therefore there no patients in this cohort. For this reason, this cohort will not be presented in any of the analyses.

Cohort-Expansion (Part B). The expansion part analysis will be presented by cancer type. The following cohorts and overall will be presented:

- Cohort 1: Pancreatic cancer
- Cohort 2: Colorectal cancer
- Cohort 3: Basket (any solid tumor type other than those included in Cohorts 1 and 2)
- Cohort-Expansion Total

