10.3 HANDLING OF MISSING DATA

Partial or missing start and end dates of AEs and concomitant medications will be imputed conservatively based on the rule described in Appendix II: Imputation rules for missing dates. The imputed dates will be used to allocate the AEs and concomitant medications to a study period, and to determine whether an AE is/is not treatment emergent. Listings of the AEs and concomitant medications will present the actual partial dates; imputed dates will not be shown in the listings.

For ORR endpoint, patients with missing data (for any reason) will be included as non-responders in the statistical analysis for each related follow-up analysis. For analyses performed in the safety population, patients who discontinue due to toxicity or clinical progression prior to post-baseline tumor assessments will be considered as non-responders and retained in the denominator.

For CBR endpoint, patients with missing data (for any reason) will be included as non-responders in the statistical analysis for each related follow-up analysis.

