- Any \geq Grade 3 non-hematological toxicity (except Grade 3 fatigue, nausea, vomiting, or diarrhea lasting $<$ 24 hours with optimal therapy, Grade 3 non-hematologic laboratory abnormalities that resolve to Grade 1 or baseline within 14 days).

All TEAEs, unless they are determined to be not related to study drug will be taken into consideration in determining DLTs. The period for DLT observation is 21 days from the start of first dose of OBI-999 (i.e., Day 1).

DLTs (not to be programmatically derived; will be analyzed as collected on eCRF) will be displayed by dose level in a frequency table in decreasing order of incidence. AEs will be graded according to the NCI CTCAE V5.0. All TEAEs unless they have been determined to be not related to study drug will be DLTs and will be summarized by dose, SOC and PT. A listing of DLTs will be prepared.

C. MTD and RP2D of OBI-999

At the time of this version of the SAP, Part A (Dose-Escalation) was completed. The RP2D of 1.2 mg/kg was identified during SRC review.

PART B (COHORT-EXPANSION)

A. Objective Response*

Overall tumor response (not to be programmatically derived; will be analyzed as collected on eCRF) will be listed by cancer type and visit. For each patient, best overall response (BOR) is defined as the best overall tumor response (complete response [CR], partial response [PR], stable disease [SD], and progressive disease [PD], or not evaluable [NE]) from the start of treatment until disease progression, recurrence or end of study. In general, the patient's best response assignment will depend on both the tumor measurement and confirmation criteria.

If an NE response is determined at a time point, this response will be ignored and subsequent non-NE responses will be used for the confirmation. For example, the sequence of tumor assessments: PR, NE, NE, CR, SD, that had more than two consecutive NEs, the third subsequent non-NE response (CR) is used as the confirmation of the first PR for best overall response derivation.

A requirement for SD is that it should be met at least once \geq 6 weeks after the first dose of trial treatment, otherwise the best response will be NE.

The criteria for confirmation of the response are summarized in the following table (Eisenhauer

et al, 2009):

Overall response first time point	Overall response subsequent time point	Best overall response
CR	CR	CR
CR	PR	SD, PD or PR [1]
CR	SD	SD provided minimum criteria for SD duration met, otherwise PD

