CR	PD	SD provided minimum criteria for SD duration met, otherwise PD
CR	NE for all subsequent time points	SD provided minimum criteria for SD duration met, otherwise NE
PR	CR	PR
PR	PR	PR
PR	SD	SD
PR	PD	SD provided minimum criteria for SD duration met, otherwise PD
PR	NE for all subsequent time points	SD provided minimum criteria for SD duration met, otherwise NE
NE	NE	NE

[1] If a CR is truly met at first timepoint, then any disease seen at a subsequent timepoint, even disease meeting PR criteria relative to baseline, makes the disease PD at that point (since disease must have re-appeared after CR). Best response would depend on whether minimum duration of SD was met. However, sometimes 'CR' may be claimed when subsequent scans suggest small lesions were likely still present and in fact the patient had PR, not CR at the first timepoint. Under these circumstances, the original CR should be changed to a PR and the best response is PR.

Objective Response Rate (ORR) is defined as the percentage of patients with confirmed PR or CR based on tumor assessment as determined by RECIST 1.1 among all the patients in the safety and efficacy populations. A confirmed response will be defined as two or more consecutive assessments separated by at least 3 weeks. For summaries in the safety population, patients who discontinue due to toxicity or clinical progression prior to post-baseline tumor assessments will be considered as non-responders and retained in the denominator. A summary with the number of patients by BOR categories, ORR and the Clopper-Pearson 95% confidence interval (CI) for the ORR will be provided.

A by-patient swim lane plot of time (weeks) to Overall Response will be provided, along with waterfall plots (bar plot) showing the best reduction in target lesion therapy will be presented for Cohort-Expansion patients.

Sample code for ORR is provided below:

```
proc freq data=data;
by cohort;
tables AVAL/binomial alpha=0.05 nocum norow;
exact binomial;
run;
```

If the BOR used for ORR based on unconfirmed and confirmed overall responses differs by 10%, then we will present the same summary for ORR based on unconfirmed overall responses as a sensitivity analysis.

B. Clinical Benefit Rate

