- In section §10.5, the protocol deviations will neither be summarized nor listed.
- In section §10.6.1, the baseline and demographic characteristics will be summarized using only the safety population and listed.
- In section §10.6.2, the medical history and current medical conditions will neither be summarized nor listed.
- In section §10.6.3, the prior and concomitant medications will neither be summarized nor listed.
- In section §10.6.4, the cancer history will be summarized using only the safety population and listed.
- In section §10.6.5, other medical history will not be listed.
- In section §10.6.6, prior cancer surgeries will neither be summarized nor listed.
- In section §10.6.7, prior cancer radiotherapy will neither be summarized nor listed.
- In section §10.6.8, prior cancer medication therapy will neither be summarized nor listed.
- In section §10.6.9, smoking history will neither be summarized nor listed.
- In section §10.7.1, adverse events that will be analyzed and listed have been marked with asterisks. Only ORR analysis using safety population and ADA analysis using safety and PK populations have been selected as CBR, DOR and PFS analyses will no longer be conducted for the aCSR. Only waterfall plot (bar plot) showing the best reduction in target lesion therapy will be presented for Cohort-Expansion patients.
- In section §10.8.1, only extent of exposure will be summarized, and all study drug administration data will be listed.
- In section §10.8.2, laboratory data will only be listed. OBI decided not to conduct normalization of local laboratory assessments; therefore, data will be listed as recorded.
- In section §10.8.3, vital signs data will only be listed.
- In section §10.8.4, electrocardiogram data will only be listed.
- In section §10.8.5, ECOG, physical examination and ophthalmological data will neither be summarized nor listed.

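### Does the missing best-overall-response rule for never-scanned patients distort the response table or the waterfall plot?

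*SAP*

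**What the plan says.** SAP 5.4 reports that "four patients did not have a RECIST post-baseline assessment and so it has been decided to replace them to have enough data", and then that "2 'replacement' patients have been enrolled in the pancreatic cohort, while searching for 2 'replacement' patients in the colorectal cohort was in progress". The study stopped before any go/no-go analysis was done.

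SAP 11 cuts the efficacy output for the abbreviated report to two items. For the table: "Only ORR analysis using safety population and ADA analysis using safety and PK populations have been selected". For the figure: "Only waterfall plot (bar plot) showing the best reduction in target lesion therapy will be presented for Cohort-Expansion patients". Clinical benefit rate (CBR), duration of response and progression-free survival are dropped.

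The retained table comes from SAP 10.7.1, which calls for "A summary with the number of patients by BOR categories, ORR and the Clopper-Pearson 95% confidence interval". The same section defines BOR for each patient as CR, PR, SD, PD or NE. On unevaluable time points it says "If an NE response is determined at a time point, this response will be ignored", with later evaluable responses used for confirmation. NE is also the result when stable disease is not met at six weeks or later, or when a CR or PR is followed only by NE.

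On missing data, SAP 10.3 says "For ORR endpoint, patients with missing data (for any reason) will be included as non-responders in the statistical analysis", and it has a matching rule for CBR. It does not mention BOR. SAP 10.1 sets the general default: "If not specified otherwise, the number of observations with non-missing values will be the denominator for percentage calculation".

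**The concern.** Every row of the BOR table in SAP 10.7.1 starts from a response recorded at a time point. A patient who never had a post-baseline scan has no such response, and no sentence assigns that patient to NE or to any other category. Version 2.0 of the SAP discloses four such patients and still adds no rule.

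One summary could then carry two denominators: assessed patients for the BOR percentages and all treated patients for the ORR. With CBR dropped, the BOR rows are the only table in which stable disease appears, so inflated percentages there would be read as a sign of disease control. In the waterfall plot an unscanned patient has no bar while the replacement has one. The pancreatic panel could therefore look like a complete stage 1 of nine patients although eleven were treated.

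**Working it through.** **The plan's own figure, for context.** SAP 7 states 72% power and one-sided alpha 0.12 for the rule of at least 1 response in 9 patients, then at least 4 in 19. The exact probability of success is the sum over x = 1 to 9 of P(X1 = x) × P(X2 ≥ 4 − x), with X1 ~ Bin(9, p) and X2 ~ Bin(10, p). It is 0.7201 at p = 0.25 and 0.1100 at p = 0.10. The power reproduces and the type I error lies within 0.12. The present question touches neither figure.

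**Inputs.** From SAP 5.4: up to 9 patients per cohort in stage 1, four without a post-baseline assessment, two pancreatic replacements enrolled and no colorectal ones. Assumptions, because the documents do not give these facts: exactly 9 original patients per cohort, all dosed; the four split 2 pancreatic and 2 colorectal, as the replacement counts suggest; both pancreatic replacements dosed and scanned; nobody else unscanned.

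- Pancreatic: treated 9 + 2 = 11; assessed 9 − 2 + 2 = 9.
- Colorectal: treated 9; assessed 9 − 2 = 7.
- All three cohorts: treated 27 + 2 = 29; assessed 29 − 4 = 25.

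**Reading 1: the unscanned patients are missing for BOR.** The percentage is k/assessed instead of k/treated.

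| Cohort | One patient, BOR row | One patient, ORR row | Ratio |
|---|---|---|---|
| Pancreatic | 1/9 = 11.1% | 1/11 = 9.1% | 11/9 = 1.22 |
| Colorectal | 1/7 = 14.3% | 1/9 = 11.1% | 9/7 = 1.29 |

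For illustration, 3 colorectal patients with SD give 3/7 = 42.9% against 3/9 = 33.3%. Five pancreatic patients with SD give 5/9 = 55.6% against 5/11 = 45.5%. If only one pancreatic replacement was scanned the pancreatic ratio is 11/8 = 1.38, and if neither was, 11/7 = 1.57.

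**Reading 2: the unscanned patients are NE.** No BOR value is missing, so the SAP 10.1 default gives 11 and 9, the same denominators as the ORR. Both ratios are 1.00.

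**Reading 3: the four were never dosed.** SAP 5.4 does not say that they were. They are then outside the safety population. Pancreatic is 7 + 2 = 9 treated and 9 assessed, colorectal 7 and 7. Both ratios are again 1.00.

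**ORR.** Between Readings 1 and 2 nothing moves, because SAP 10.3 and 10.7.1 fix the denominator. With no responders, the Clopper-Pearson upper limit is 1 − 0.025^(1/n): 33.6% for n = 9 and 28.5% for n = 11.

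**Waterfall plot.** Under SAP 9 the efficacy population is the safety population less patients with no follow-up scan. Those patients have no post-baseline measurement and hence no bar. Under the assumptions above, 25 bars are drawn and 4 of 29 patients (13.8%) have none, whichever population is named.

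**The case for a change.** The best case for a change is that the text permits both Reading 1 and Reading 2, so two programmers could produce different tables from it. The output concerned is one of the few kept. Denominators of this kind do matter: protocol 4.4 reports 5 patients with stable disease in Part A, which is 5/13 = 38.5% of those assessed or 5/15 = 33.3% of those enrolled. A single sentence would remove the doubt.

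The silence on the BOR category is real, and that much stands. The rest carries less weight:

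- BOR is defined for each patient over a closed list. A treated patient without a scan cannot be CR, PR, SD or PD, so NE is what remains. The SAP already uses NE where a response cannot be established.
- SAP 10.7.1 asks for numbers of patients by category. Percentages enter only through the general convention in SAP 10.1, and the counts would show any shortfall against the cohort size.
- SAP 10.4 tabulates the safety and efficacy populations by cohort, and SAP 11 does not cut that section. Under the assumptions above it would show 11 treated and 9 scanned pancreatic patients, which is what a footnote to the figure would say.
- The Part A figures are background in the protocol, with both 13 and 15 stated. They are not an output of this table.

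Some loose wording remains. SAP 9 still calls the efficacy population primary for clinical activity, but SAP 11 selects the safety population for the ORR. The CBR clause keeps never-assessed patients in the denominator of a population that excludes them, but CBR is no longer reported. SAP 11 does not list the replacement of unscanned patients, for which the protocol has no Part B rule, but SAP 5.4 and the revision history both disclose it. These points are editorial.

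**Conclusion.** No change to the plan is needed. The SAP leaves out one coding detail, and an analyst would supply it by entering never-scanned treated patients as NE or in a row of their own. The BOR and ORR denominators then agree.

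The contrary reading would raise BOR percentages by a factor of 1.22 in the pancreatic cohort and 1.29 in the colorectal cohort. Those factors rest on cohort sizes, a two-and-two split, and dosing and scanning of patients that the documents do not confirm. With nine original patients per cohort the pancreatic factor runs from 1.00 to 1.57 and the colorectal factor from 1.00 to 1.29. If the four were dosed, the ORR and its interval are the same however BOR is coded. If they were not, they fall outside the safety population and the question does not arise. The waterfall bars do not depend on the population named, and no stage 1 decision was made that could have been affected. The table and figure shells are in a separate document that was not available and may already settle the point.
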